### **13.9 Appendix 9: Participant Reminder Card**

## Appendix 10. Participant Reminder Card

Participant ID: \_\_\_\_\_ Date of Study Treatment \_\_\_\_\_

Site of Injection:     Right Arm    Left Arm    Right Leg    Left Leg

**Instructions:** Please complete this reminder card in the evening after and for three days following your study treatment. The “Evening of study treatment” column should include any side effects from the time you received the study treatment until 11:59pm of that day. Days 1, 2 and 3 should include any side effects from midnight (12:00 am) to 11:59 pm of that day (1 day, 2 days or 3 days after receiving the study treatment).

Take this card with you to your next study visit for review with the study team. If you have any questions, or if you have any concerns or side effects that you’d like to discuss, please contact your study team.

To describe the size of any area that is red or swollen, please use the measuring tool provided with this reminder card to indicate the approximate size of a circle that could fully cover the area of redness or swelling.

Possible side effects	Evening of study treatment	1 day after study treatment	2 days after study treatment	3 days after study treatment	Date Resolved
Redness or bruising at treatment site	 None  Diameter (in cm) from measuring tool: _____  Greater than 7cm	 None  Diameter (in cm) from measuring tool: _____  Greater than 7cm	 None  Diameter (in cm) from measuring tool: _____  Greater than 7cm	 None  Diameter (in cm) from measuring tool: _____  Greater than 7cm	<hr/> If date unknown:  1 week**  2 weeks**  3 weeks**
Pain at treatment site	 None  A little, controlled with OTC* meds  A lot, OTC meds didn’t work, prevented normal activity	 None  A little, controlled with OTC* meds  A lot, OTC meds didn’t work, prevented normal activity	 None  A little, controlled with OTC* meds  A lot, OTC meds didn’t work, prevented normal activity	 None  A little, controlled with OTC* meds  A lot, OTC meds didn’t work, prevented normal activity	<hr/> If date unknown:  1 week**  2 weeks**  3 weeks**
Swelling/ Edema at treatment site	 None  Diameter (in cm) from measuring tool: _____  Greater than 7cm	 None  Diameter (in cm) from measuring tool: _____  Greater than 7cm	 None  Diameter (in cm) from measuring tool: _____  Greater than 7cm	 None  Diameter (in cm) from measuring tool: _____  Greater than 7cm	<hr/> If date unknown:  1 week**  2 weeks**  3 weeks**
Oral Temperature	Please record below:  °F _____  °C	Please record below:  °F _____  °C	Please record below:  °F _____  °C	Please record below:  °F _____  °C	

\* OTC – Over the counter analgesics or painkillers such as paracetamol, acetaminophen (e.g. Tylenol®) or ibuprofen (e.g. Advil® or Motrin®).

\*\* After study treatment

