**Table 6.1: Grading Scale for Injection Site Reactions**

Local Reaction to Injectable Product (Grade)	Mild(1)	Moderate(2)	Severe(3)	Potentially Life Threatening(4)
Pain	Does not interfere with activity	Repeated use of non-narcotic pain reliever >24 hours or interferes with activity	Any use of narcotic pain reliever or prevents daily activity	Emergency room (ER) visit or hospitalization
Tenderness	Mild discomfort to touch	Discomfort with movement	Significant discomfort at rest	ER visit or hospitalization
Erythema/Redness*	2.5-5 cm	5.1-10 cm	>10 cm	Necrosis or exfoliative dermatitis
Induration/Swelling**	2.5-5 cm and does not interfere with activity	5.1-10 cm or interferes with activity	>10 cm or prevents daily activity	Necrosis

\* September 2007 “FDA Guidance for Industry—Toxicity Grading Scale for Healthy Adult and Adolescent Volunteers Enrolled in Preventive Vaccine Clinical Trials”

\*in addition to grading the measured local reaction at the greatest single diameter, the measurement should be recorded as a continuous variable.

\*\*Induration/Swelling should be evaluated and graded using the functional scale as well as the actual measurement.

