**Did you have any other side effects?**

Other side effects (insert below)	Evening of study treatment	1 day after study treatment	2 days after study treatment	3 days after study treatment	Date Resolved
	 Mild, barely noticeable  Moderate, slowed me down  Severe	 Mild, barely noticeable  Moderate, slowed me down  Severe	 Mild, barely noticeable  Moderate, slowed me down  Severe	 Mild, barely noticeable  Moderate, slowed me down  Severe	<hr/> If date unknown:  1 week**  2 weeks**  3 weeks**
	 Mild, barely noticeable  Moderate, slowed me down  Severe	 Mild, barely noticeable  Moderate, slowed me down  Severe	 Mild, barely noticeable  Moderate, slowed me down  Severe	 Mild, barely noticeable  Moderate, slowed me down  Severe	<hr/> If date unknown:  1 week**  2 weeks**  3 weeks**

\*\* After study treatment

Did you contact the study team for any symptoms that were not listed here or the severity was worse than the available choices?  Yes  No

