**About Injection Site Reaction**

The most common reactions to the study treatment are reactions at the injection site such as an area of redness, a little bruising, possible swelling, and temporary pain. For most people, it is not bothersome at all and disappears in a day or two. However, it may last a week or more.

If you have any concerns about your symptoms, have any ongoing injection site reactions or side effects that are still present more than 3 days after the study treatment, please contact your study team.

Coordinator Name: \_\_\_\_\_

Coordinator Telephone Number: \_\_\_\_\_

Did you take any medications for your injection site reactions or other symptoms?

Yes (record below)  No

Is there anything else that you would like to discuss with the study team?

Yes (record below)  No

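### The Participant Reminder Card does not collect what Table 6.1 needs to grade injection site reactions, so some grades for primary endpoint 2 and for site-reaction ERERs will rest on recall

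*Combined protocol and SAP*

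**What the plan says.** Section 6.6 gives investigators Table 6.1 for grading site reactions. Erythema and induration are graded by size: Grade 1 is 2.5 to 5 cm, Grade 2 is 5.1 to 10 cm, Grade 3 is above 10 cm. Induration is also graded by its effect on activity, and a footnote requires both the functional scale and the measurement. Another footnote, which the asterisks appear to tie to erythema, says that "in addition to grading the measured local reaction at the greatest single diameter, the measurement should be recorded as a continuous variable". Tenderness is an item of its own. Pain is Grade 2 if it interferes with activity or needs repeated non-narcotic relief for more than 24 hours. It is Grade 3 if it prevents daily activity or needs any narcotic.

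The card in Appendix 9 covers the evening of treatment and the next three days. The first row is "Redness or bruising at treatment site". It and the swelling row offer none, a diameter read from a supplied tool, or "Greater than 7cm". The pain row offers none, "A little, controlled with OTC* meds", or a top option that joins a lot of pain, failed over-the-counter medication and "prevented normal activity". Temperature has a row and other side effects have free-text rows.

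Primary endpoint 2 (Section 3) names four reactions: erythema, induration, tenderness and pain. Section 8.2 tabulates them by type and grade. Under Section 7.5.2, any of the four at Grade 3 or above is an ERER if recorded an hour or more after treatment.

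**The concern.** The card and the grading table belong to the same protocol and describe the same reactions, but the card's answers do not map to the table's grades. The mismatch falls in the period that matters most for these data. Direct observation ends 30 to 45 minutes after each treatment (Section 7.3), before the one-hour point from which a site reaction can be an ERER. From then until the next contact, the card is the only scheduled record made at the time.

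At stake is how well founded the grades are in the primary endpoint 2 table, and whether a site reaction is correctly placed on either side of the Grade 3 line. An investigator can grade only what was written down, what can still be seen, or what the subject remembers.

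**Working it through.** There is no plan figure to reproduce. The check sets the card against Table 6.1.

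**Size.** Inputs are the Table 6.1 bands and the card's box. A written diameter of 7 cm or less falls in one place only: below Grade 1, Grade 1 or Grade 2. A bare tick above 7 cm covers 7.1 to 10 cm (Grade 2) and anything above 10 cm (Grade 3). The box opens 10 − 7 = 3 cm below the Grade 2/3 boundary. Without a number, that boundary cannot be read and the continuous measurement is lost. Grade 4 is defined by tissue damage, not size, so the box does not identify it either.

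**Item by item.**

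| Endpoint 2 reaction | What Table 6.1 needs | What the card lacks |
|---|---|---|
| Erythema | Diameter, with a cut at 10 cm | A cut at 10 cm; redness kept apart from bruising |
| Induration | Diameter and effect on activity | A cut at 10 cm; any question on activity |
| Tenderness | Its own grade, from discomfort on touch to marked discomfort at rest | A row |
| Pain | Interference (Grade 2) told apart from prevention (Grade 3) | An option for interference alone |

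All 4 of the 4 reactions have at least one gap. For example, a 4 cm swelling that prevents daily activity is Grade 3 in Table 6.1, but the card's swelling row would show only 4 cm, which is Grade 1 by size.

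**Timing.** Weeks 2, 6, 10 and 14 may be telephone contacts (Section 6.1.2).
- After dose 1, the next contact is Week 2 ± 1 week, that is Day 7 to Day 21.
- After dose 2, with windows counted from Day 0, the dose falls on Day 21 to 35 and the next contact on Day 35 to 49. The nominal gap is 14 days and the range is 35 − 35 = 0 to 49 − 21 = 28 days. Doses 3 and 4 follow the same pattern.

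On the nominal schedule, review therefore comes well after the card's last day, and a short-lived reaction may have gone.

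**Which scale applies.** Sections 6.2.4.3 and 6.6 grade local reactions on the vaccine-trial scale reproduced in Table 6.1. Section 6.2.4.4, the card's own section, judges whether an entry reaches Grade 1 against CTCAE v4.0. The injection site reaction row in Appendix 4 has no diameter cut at all. The two instructions can therefore give different answers for the same entry.

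**The case against.** The strongest reply is that this is a memory aid, not a grading form. Table 6.1 and its footnotes are addressed to the investigator, and nothing obliges the card to reproduce them. Section 6.2.4.4 expects card and final grade to differ at times and asks for the reasoning in source documents.

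There are also real backstops:
- The diameter field has no stated upper limit, so a subject can write a number above 7 cm. The range of the measuring tool is not given.
- Tenderness can go in the free-text rows.
- The card asks whether the subject contacted the team about "any symptoms that were not listed here or the severity was worse than the available choices", and says that for "side effects that are still present more than 3 days after the study treatment, please contact your study team".
- It asks "Did you take any medications for your injection site reactions or other symptoms", and ticks for over-the-counter use on successive days partly reveal the repeated-analgesic route to Grade 2 pain.
- Section 7.3 has subjects reminded to report events at once. A site-reaction assessment is required even at telephone visits, and an office visit may follow.

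Much of this stands. Size is ambiguous only when the box is ticked without a number, and the pain gap concerns the interference route only. The backstops reduce the problem but do not remove it. Each depends on the subject taking the initiative or on memory at review, and none supplies on the day the item that was not asked for.

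**Conclusion.** The mismatch is plain from the text and touches all four reactions in primary endpoint 2. Its consequence is modest: for some reactions, the investigator's grade will rest on what the subject recalls at review. How many cannot be estimated. The documents give no rate of reactions above 7 cm, and Section 1.3.1 says only that related Grade 3 events with VGX-3100 were very few, without a count. Severity is minor.

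Two stronger readings are tempting, and the documents support neither.

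- A reader might infer that the card delays recognition of an ERER or its 72-hour notice. The interval to the next contact is set by the visit schedule, and a card matching Table 6.1 exactly would be reviewed on the same days. Section 7.5.2 also does not say when the 72 hours begin.
- A reader might infer that the pausing rule in Section 7.5.3.1 is undermined. With 10 subjects it needs 4 of them (10/3 = 3.3, rounded up). It counts every kind of related ERER, including fever and systemic symptoms, and no document gives a rate from which an effect could be worked out. None is shown.

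The conclusion assumes that sites follow the schedule as written and that some subjects tick the top box without adding a number.

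**What to change.** Align the card with Table 6.1 and leave grading with the investigator.

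1. Ask for the measured diameter in cm at every size, using a tool that reads beyond 10 cm. If a top box is kept, set it above 10 cm and still ask for the number.
2. Record redness separately from bruising.
3. For swelling and for pain, ask whether it interfered with daily activity or prevented it.
4. Add a tenderness row using the Table 6.1 descriptors.
5. Reconcile Section 6.2.4.4 with Sections 6.2.4.3 and 6.6, so that one stated scale applies when card entries on local reactions are judged.

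The cost is a revised subject-facing form, possibly a new measuring tool, IRB submission, a short clarification to the protocol text and slightly more for subjects to complete. No visits, staff or procedures are added.

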**Did you have any other side effects?**

Other side effects (insert below)	Evening of study treatment	1 day after study treatment	2 days after study treatment	3 days after study treatment	Date Resolved
	 Mild, barely noticeable  Moderate, slowed me down  Severe	 Mild, barely noticeable  Moderate, slowed me down  Severe	 Mild, barely noticeable  Moderate, slowed me down  Severe	 Mild, barely noticeable  Moderate, slowed me down  Severe	<hr/> If date unknown:  1 week**  2 weeks**  3 weeks**
	 Mild, barely noticeable  Moderate, slowed me down  Severe	 Mild, barely noticeable  Moderate, slowed me down  Severe	 Mild, barely noticeable  Moderate, slowed me down  Severe	 Mild, barely noticeable  Moderate, slowed me down  Severe	<hr/> If date unknown:  1 week**  2 weeks**  3 weeks**

\*\* After study treatment

Did you contact the study team for any symptoms that were not listed here or the severity was worse than the available choices?  Yes  No

**About Injection Site Reaction**

The most common reactions to the study treatment are reactions at the injection site such as an area of redness, a little bruising, possible swelling, and temporary pain. For most people, it is not bothersome at all and disappears in a day or two. However, it may last a week or more.

If you have any concerns about your symptoms, have any ongoing injection site reactions or side effects that are still present more than 3 days after the study treatment, please contact your study team.

Coordinator Name: \_\_\_\_\_

Coordinator Telephone Number: \_\_\_\_\_

Did you take any medications for your injection site reactions or other symptoms?

Yes (record below)  No

Is there anything else that you would like to discuss with the study team?

Yes (record below)  No

### 13.10 Appendix 10: RECIST

- A. Response will be evaluated in this study using the international criteria proposed by the Response Evaluation Criteria in Solid Tumors (RECIST) guideline (version 1.1). Changes in the largest diameter (unidimensional measurement) of the tumor lesions and the shortest diameter in the case of malignant lymph nodes are used in the RECIST criteria:

i. Definitions

Evaluable for Target Disease response: Only those participants who have measurable disease present at baseline, have received at least one cycle of therapy, and have had their disease re-evaluated will be considered evaluable for target disease response. These participants will have their response classified according to the definitions stated below. (Note: Participants who exhibit objective disease progression prior to the end of cycle 1 will also be considered evaluable.)

Evaluable Non-Target Disease Response: Participants who have lesions present at baseline that are evaluable but do not meet the definitions of measurable disease, have received at least one cycle of therapy, and have had their disease re-evaluated will be considered evaluable for non-target disease. The response assessment is based on the presence, absence, or unequivocal progression of the lesions.

ii. Disease Parameters

Measurable disease. Measurable lesions are defined as those that can be accurately measured in at least one dimension (longest diameter to be recorded) as  $\geq 20$  mm by chest x-ray or  $\geq 10$  mm with CT scan, MRI, or calipers by clinical exam. All tumor measurements must be recorded in millimeters (or decimal fractions of centimeters).

Malignant lymph nodes. To be considered pathologically enlarged and measurable, a lymph node must be  $\geq 15$  mm in short axis when assessed by CT scan (CT scan slice thickness recommended to be no greater than 5 mm). At baseline and in follow-up, only the short axis will be measured and followed.

Non-measurable disease. All other lesions (or sites of disease), including small lesions (longest diameter  $< 10$  mm or pathological lymph nodes with  $\geq 10$  to  $< 15$  mm short axis), are considered non-measurable disease. Bone lesions, leptomeningeal disease, ascites, pleural/pericardial effusions, lymphangitis cutis/pulmonitis, inflammatory breast disease, abdominal masses (not followed by CT or MRI), and cystic lesions are all considered non-measurable.

Note: Cystic lesions that meet the criteria for radiographically defined simple cysts should not be considered as malignant lesions (neither measurable nor non-measurable) since they are, by definition, simple cysts.

‘Cystic lesions’ thought to represent cystic metastases can be considered as measurable lesions, if they meet the definition of measurability described above. However, if non-cystic lesions are present in the same participant, these are preferred for selection as target lesions.

Target lesions. All measurable lesions up to a maximum of 2 lesions per organ and 5 lesions in total, representative of all involved organs, should be identified as **target lesions** and recorded and measured at baseline. Target lesions should be selected on the basis of their size (lesions with the longest diameter), be representative of all involved organs, but in addition should be those that lend themselves to reproducible repeated measurements. It may be the case that, on occasion, the largest lesion does not lend itself to reproducible measurement in which circumstance the next largest lesion which can be measured reproducibly should be selected. A sum of the diameters (longest for non-nodal lesions, short axis for nodal lesions) for all target lesions will be calculated and reported as the baseline sum diameters. If lymph nodes are to be included in the sum, then only the short axis is added into the sum. The baseline sum diameters will be used as reference to further characterize any objective tumor regression in the measurable dimension of the disease.

Non-target lesions. All other lesions (or sites of disease) including any measurable lesions over and above the 5 target lesions should be identified as **non-target lesions** and should also be recorded at baseline. Measurements of these lesions are not required, but the presence, absence, or in rare cases unequivocal progression of each should be noted throughout follow up.

### iii. Response Criteria

Complete Response (CR): Disappearance of all target lesions. Any pathological lymph nodes (whether target or non-target) must have reduction in short axis to <10 mm.

Partial Response (PR): At least a 30% decrease in the sum of the diameters of target lesions, taking as reference the baseline sum diameters.

Progressive Disease (PD): At least a 20% increase in the sum of the diameters of target lesions, taking as reference the smallest sum on study (this includes the baseline sum if that is the smallest on study). In addition to the relative increase of 20%, the sum must also demonstrate an absolute increase of at least 5 mm. (Note: the appearance of one or more new lesions is also considered progressions).

Stable Disease (SD): Neither sufficient shrinkage to qualify for PR nor sufficient increase to qualify for PD, taking as reference the smallest sum diameters while on study.

iv. Evaluation of Non-Target Lesions

Complete Response (CR): Disappearance of all non-target lesions and normalization of tumor marker level. All lymph nodes must be non-pathological in size (<10 mm short axis).

Note: If tumor markers are initially above the upper normal limit, they must normalize for a patient to be considered in complete clinical response.

Non-CR/Non-PD: Persistence of one or more non-target lesion(s) and/or maintenance of tumor marker level above the normal limits.

Progressive Disease (PD): Appearance of one or more new lesions and/or *unequivocal progression* of existing non-target lesions. *Unequivocal progression* should not normally trump target lesion status. It must be representative of overall disease status change, not a single lesion increase.

Although a clear progression of “non-target” lesions only is exceptional, the opinion of the treating physician should prevail in such circumstances, and the progression status should be confirmed at a later time by the review panel (or Principal Investigator).

v. Evaluation of New Lesions

The finding of a new lesion should be unequivocal (i.e. not due to difference in scanning technique, imaging modality, or findings thought to represent something other than tumor (for example, some ‘new’ bone lesions may be simply healing or flare of pre-existing lesions). However, a lesion identified on a follow-up scan in an anatomical location that was not scanned at baseline is considered new and will indicate PD. If a new lesion is equivocal (because of small size etc.), follow-up evaluation will clarify if it truly represents new disease and if PD is confirmed, progression should be declared using the date of the initial scan on which the lesion was discovered.

vi. Evaluation of Best Overall Response

The best overall response is the best response recorded from the start of the treatment until disease progression/recurrence (taking as reference for progressive disease the smallest measurements recorded since the treatment started). The

patient's best response assignment will depend on the achievement of both target and non-target disease.

**Time point response: patients with target (+/- non-target disease)**

Target Lesions	Non-Target Lesions	New Lesions	Overall Response
CR	CR	No	CR
CR	Non-CR/Non-PD	No	PR
CR	Not evaluated	No	PR
PR	Non-CR/Non-PD/not evaluated	No	PR
SD	Non-CR/Non-PD/not evaluated	No	SD
PD	Any	Yes or No	PD
Any	PD	Yes or No	PD
Any	Any	Yes	PD

**Time point response: patients with non-target disease only**

Non-Target Lesions	New Lesions	Overall Response
CR	No	CR
Non-CR/non-PD	No	Non-CR/non-PD*
Not all evaluated	No	not evaluated
Unequivocal PD	Yes or No	PD
Any	Yes	PD
* 'Non-CR/non-PD' is preferred over 'stable disease' for non-target disease since SD is increasingly used as an endpoint for assessment of efficacy in some trials so to assign this category when no lesions can be measured is not advised		

vii. Confirmation/Duration of Response

**Confirmation:** Confirmation of PR and CR is required to ensure responses identified are not the results of measurement error. This will also permit appropriate interpretation of results in the context of historical data where response has traditionally required confirmation.

**Duration of overall response:** The duration of overall response is measured from the time measurement criteria are met for CR or PR (whichever is first recorded) until the first date that recurrent or progressive disease is objectively documented (taking as reference for progressive disease the smallest measurements recorded on study)

Duration of overall complete response: The duration of overall CR is measured from the time measurement criteria are first met for CR until the first date that recurrent disease is objectively documented.

Duration of stable disease: Stable disease is measured from the start of the treatment until the criteria for progression are met, taking as reference the smallest sum on study (if baseline sum is the smallest, this is the reference for calculation of PD).

- B. Progression Free Survival**- any progression of disease as defined below will be recorded and summarized for subjects in the individual cohorts and overall

Overall Survival: Overall Survival (OS) is defined as the time from randomization (or registration) to death due to any cause, or censored at date last known alive.

Progression-Free Survival: Progression-Free Survival (PFS) is defined as the time from randomization (or registration) to the earlier of progression or death due to any cause. Participants alive without disease progression are censored at date of last disease evaluation.

Time to Progression: Time to Progression (TTP) is defined as the time from randomization (or registration) to progression, or censored at date of last disease evaluation for those without progression reported
